# 9.3.3 ANALYSIS OF THE SECONDARY ENDPOINT(S)

Fragmentation speed, energy utilization, lasing activity, operative time, lasing time, lithotripsy time, and treatment time will be analyzed using Kruskal-Wallis statistical tests and multivariate regression to predict differences in levels of renal-damage associated biomarkers.

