# 1.1 SYNOPSIS

Title:	SUPERPULSED THULIUM FIBER LASER VS. PULSE MODULATED HIGH POWER HOLMIUM: YAG LASER FOR RETROGRADE INTRARENAL SURGERY
Grant Number:	N/A
Study Description:	
 
This is a randomized prospective study comparing the stone free rate and operative efficiency of two leading contemporary laser systems used during retrograde intrarenal surgery for kidney stone disease. We will compare the following two systems:
 
1. A superpulsed thulium fiber laser (thulium)
 
2. A pulse modulated high power holmium laser (Holmium)
 

Objectives * :	Aim: To determine which laser system has superior outcomes as measured by post-operative stone-free status and intraoperative efficiency metrics
	Research Question: During retrograde intrarenal surgery for kidney stone disease, which contemporary laser system (thulium vs. holmium) has a superior stone free rate?
	Null hypothesis: During retrograde intrarenal surgery for kidney stone disease, there is no difference in stone free rates between the two laser systems.
	Alternative Hypothesis: During retrograde intrarenal surgery for kidney stone disease, the thulium laser has a superior stone free rate.
Endpoints * :	
 
Primary Endpoint:
 
Stone-free status as determined by a post-operative CT scan.
 

	
 
Secondary Endpoints:
 
The secondary endpoints to be collected will pertain to efficiency metrics as produced by the laser systems: 
 
Fragmentation speed = stone volume/lasing time (mm3/sec)
 
Energy Utilization = Laser energy/volume of stone (J/mm3)
 
Lasing Activity: Lasing time/lithotripsy operative time (%)
 
Operative time (minutes)
 
Lasing time (seconds)
 
Lithotripsy operating time (seconds)
 
Treatment time (seconds)
 
 
 

Study Population:	We anticipate a sample size of 82 subjects enrolled in this study. Adult patients 18-years of age and older with non-obstructing kidney stones undergoing planned retrograde intrarenal surgery with laser lithotripsy.
Description of Sites/Facilities Enrolling Participants:	[name] currently operates twice a week at Mount Sinai West (formerly Mount Sinai Roosevelt Hospital), located at [name]. In addition, he sees patients in the clinic at the following sites: Department of Urology Faculty Practice at [name]; Midtown Urology FPA at [name].

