# **3** OBJECTIVES AND ENDPOINTS

OBJECTIVES	ENDPOINTS	JUSTIFICATION FOR	PUTATIVE
		ENDPOINTS	MECHANISMS OF
			ACTION
Primary			
To determine which laser	Stone free status as	Stone free status on 2 month	N/A
system (if any) offers superior	determined by 2-	follow up CT scan is the most	
efficacy.	month postoperative	accurate evaluation for complete	
	CT scan	resolution of a patient's kidney	
		stone burden	

OBJECTIVES	ENDPOINTS	JUSTIFICATION FOR	PUTATIVE
		ENDPOINTS	MECHANISMS OF
			ACTION
Secondary			
To determine which laser system (if any) offers superior efficiency.	Fragmentation speed, lasing activity, and energy utilization	These intraoperative laser metrics allow for the evaluation of intraoperative laser efficiency	N/A

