# **5 STUDY POPULATION**

#### 5.1 INCLUSION CRITERIA

- Undergoing single stage unilateral RIRS for total stone burden volume >5mm to < 20 mm
- Must have preop CT scan to measure HU and measurements

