## 5.2 EXCLUSION CRITERIA

- Anatomic variations: horseshoe kidney, pelvic kidney, ptotic kidney, urinary diversion or ureteral stricture
- Ureteral stent
- Uric acid component >50% on stone analysis
- Prior ureteroscopy within 6 weeks of current surgery
- Irreversible coagulopathy
- Urothelial tumor(s), direct extraction of the stone(s) without needing laser lithotripsy, and failure to reach the stone in the upper urinary tract with the ureteroscope.

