## 6 STUDY INTERVENTION(S) OR EXPERIMENTAL MANIPULATION(S)

## 6.1 STUDY INTERVENTION(S) OR EXPERIMENTAL MANIPULATION(S) ADMINISTRATION

#### 6.1.1 STUDY INTERVENTION OR EXPERIMENTAL MANIPULATION DESCRIPTION

For subjects receiving URS, randomization will occur preoperatively. These subjects will be randomized to undergo lithotripsy with either Ho:YAG or TFL lasers.

All subjects will undergo surgical interventions that abide by broadly accepted guidelines and standards of care, allowing for slight variations in technique as seen necessary by the attending surgeon [name].

The type of laser that is chosen in SOC is based on hospital availability. That is, most hospitals only have one laser type to choose from (and that laser type is generally contingent on the biomedical contracts the

hospital holds with the various laser manufacturers). We are uniquely situated at Mount Sinai West in that we have multiple laser systems to choose from. Multiple surgeons share the lasers, and typically [name] will use whichever laser is already in the room or readily available. Approximately 50% of ureteroscopies were performed with each laser, +/- 10%.

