## 9 STATISTICAL CONSIDERATIONS

## 9.1 SAMPLE SIZE DETERMINATION

A sample size of 82 patients will be accrued locally. We are enrolling 82 patients to allow for any potential exclusions due to failure to follow up. Ulvik et.al found a stone free rate of 66% and 33% respectively for the thulium fiber laser and holmium laser respectively. Our statistical analysis is to evaluate the superiority of the two laser modalities regarding stone free rate. With an allocation ratio of 1:1, 80% power, alpha of 5%, 66% stone free success of the thulium fiber laser, and 33% stone free success of the holmium laser, our sample size is 33 in each study arm for a total of 66 patients. Based on these calculations and factoring in a 20% dropout rate, we seek to enroll 82 total patients.

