## 9.2 POPULATIONS FOR ANALYSES

All enrolled subjects will be included for analyses.

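### Section 9.3.3 aims its only regression for the efficiency metrics at biomarkers that are never defined, and specifies no arm effect or confidence interval for any of the seven metrics

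*Combined protocol and SAP*

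**What the plan says.** The secondary objective in Section 3 is a comparison of the two lasers: "To determine which laser system (if any) offers superior efficiency". The Synopsis lists seven efficiency metrics as secondary endpoints, and Section 3 names three of them. Neither lists a biomarker.

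Section 9.3.3 is a single sentence. It assigns all seven metrics to Kruskal-Wallis tests and "multivariate regression to predict differences in levels of renal-damage associated biomarkers". It gives no covariates, scale, arm term, effect measure or interval. The regressions in Sections 9.3.1 and 9.3.2 concern stone-free rate.

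Other text bears on how to read the sentence and on how to repair it:

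- The schedule in Section 1.3 has no row for urine or biomarkers. Section 7.2 nevertheless covers what happens to urine samples on withdrawal, and Section 10.1.3 covers their storage. Section 10.1.3.1 mentions laboratory data in general terms.
- Section 5.1 already requires baseline imaging: "Must have preop CT scan to measure HU and measurements".
- Section 6.1.1 states that "randomization will occur preoperatively". Section 5.2 excludes "direct extraction of the stone(s) without needing laser lithotripsy". Section 9.2 states: "All enrolled subjects will be included for analyses".

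**The concern.** The sentence in Section 9.3.3 can be read in two ways, and neither gives the comparison that the objective needs.

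- **The biomarkers are the outcome.** The regression then has an outcome with no analyte, assay or time point, and the efficiency metrics may even be its predictors. It would not say which laser is more efficient.
- **The metrics are the outcomes and the ending is stray text.** The regression then still lacks covariates, a scale and a stated arm effect.

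At stake is the size of the answer. The plan specifies no estimate of how much faster or more energy-efficient one laser is, and no interval around it. Model, scale and covariates could be chosen for seven metrics after the data are seen.

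**Working it through.** **1. The plan's own figures.** Section 9.3.3 gives none. The numbers per arm used below come from Section 9.1. With 66% against 33%, 80% power and 5% alpha (taken as two-sided, since the plan does not say), the unpooled formula gives

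n = (1.960 + 0.842)² × (0.66×0.34 + 0.33×0.67) / 0.33² = 7.849 × 0.4455 / 0.1089 = 32.1, so 33 per arm and 66 in total.

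Then 66 / 0.8 = 82.5, against the stated 82, which is 41 per arm. The figure reproduces to within rounding.

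**2. Is the regression outcome defined?**

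| Place | Biomarker or urine content |
|---|---|
| Synopsis, secondary endpoints | none |
| Section 1.3 schedule | none |
| Section 3 objectives table | none |
| Sections 7.2 and 10.1.3 | urine samples mentioned; no analyte, assay or time point |
| Section 9.3.3 | biomarkers named as what the regression predicts |

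The outcome is named once and defined nowhere.

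**3. What do the rank tests supply?** With two groups, Kruskal-Wallis is the two-sided Wilcoxon rank-sum test. On one simulated data set both gave p = 0.0251. In simulations with no true difference (5,000 runs per case) its type I error was 4.5% to 5.4%, so it is valid. Its output is a statistic and a p-value.

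**4. What would adjustment add?** The documents give no SD for any metric and no correlation r between CT values and a metric. Results are therefore in SD units, and r is an assumption.

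- Unadjusted 95% CI half-width at 41 per arm: 1.990 × √(2/41) = 0.44 SD.
- With three covariates and N patients in total, the ratio of adjusted to unadjusted width is √[(1 − r²)(N − 3)/(N − 6)] × t(N − 5)/t(N − 2).
- At N = 82 the part that does not depend on r is √(79/76) × 1.9913/1.9901 = 1.020.

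| Assumed r | Ratio, N = 82 | Change in width | Half-width | Change in width, N = 66 |
|---|---|---|---|---|
| 0 | 1.020 | 2.0% wider | 0.45 SD | 2.6% wider |
| 0.3 | 0.954 × 1.020 = 0.973 | 2.7% narrower | 0.43 SD | 2.2% narrower |
| 0.5 | 0.866 × 1.020 = 0.883 | 11.7% narrower | 0.39 SD | 11.2% narrower |
| 0.7 | 0.714 × 1.020 = 0.729 | 27.1% narrower | 0.32 SD | 26.8% narrower |

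Simulation at 41 per arm (10,000 runs per case) gave 2.7%, 11.6% and 27.2% for r = 0.3, 0.5 and 0.7.

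The metrics are recorded at surgery, while Section 9.1 ties the extra enrolment to later loss: "We are enrolling 82 patients to allow for any potential exclusions due to failure to follow up". That is why 41 per arm is used first. It is an upper bound, because patients who are not lased or are excluded during surgery would reduce it.

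**5. Zero lasing time.** Fragmentation speed divides by lasing time, and the logarithm of zero does not exist, so these metrics cannot be computed for a patient who is not lased. The documents give no rate. At an assumed 2%, 5% or 10% of 82 patients, about 2, 4 or 8 are affected. The chance of at least one is 1 − 0.98⁸² = 81%, 1 − 0.95⁸² = 98.5%, or above 99.9%.

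**The case against.** The strongest reply has four parts.

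- **A regression is planned, and any fitted regression yields coefficients and intervals.** This stands as a limit on the point. A reader might infer that the efficiency objective can produce no estimate at all, but the documents do not support that. The gap is that no estimate or interval is specified for the arm comparison.
- **The precision figures measure something other than the defect.** This stands too. They describe the gain from adjustment under an assumed r. Fragmentation speed and energy utilization, two of the three metrics in Section 3, are already scaled by stone volume, so the gain there may be small. Nothing in the documents shows that CT values predict lasing activity. An unadjusted difference with an interval would close the main gap.
- **Leaving out patients who were not lased has its own problem.** The decision to lase comes after randomization and is made by an operator who, per Section 6.3, cannot be blinded. This stands, and counts alone do not remove the possible bias. The fix therefore labels those analyses as conditional.
- **Two analyses per metric could disagree.** This stands unless the plan says which one is the test. The fix does so.

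A reader might also take the ending as plainly a paste error, or as proof of an undisclosed urine study. The urine text in Sections 7.2 and 10.1.3 argues against the first. The endpoints and schedule, which contain no urine or biomarker item, argue against the second. The laboratory wording in Section 10.1.3.1 is too general to decide. Only the sponsor can settle it.

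**Conclusion.** The point holds and should be fixed. The regression in Section 9.3.3 names an outcome that is not an endpoint, is not scheduled and is not defined, so as written it does not compare the lasers on efficiency. For all seven metrics the plan specifies no arm-effect estimate and no confidence interval. This rests on the text alone and needs no assumption.

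The further benefit of adjustment is conditional on r and ranges from a 2% wider interval to one about 27% narrower at 41 per arm. It is not what makes the point. A reader might infer that the planned rank tests are biased or invalid, but neither the documents nor the simulations support that. Because Kruskal-Wallis stays as the test, no gain in power is claimed. The primary endpoint and the sample size are unaffected.

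**What to change.** Replace the regression clause in Section 9.3.3 with: *Each efficiency metric will also be regressed on laser arm, adjusted for baseline stone volume, number of stones and HU from the pre-operative CT, and the arm effect reported with a 95% CI.* Then state the following.

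- **Roles.** The Kruskal-Wallis test remains the test. The regression supplies the estimate and interval.
- **Scale.** Use logs for time, speed and energy metrics, with log stone volume as covariate, so that the arm effect is a ratio of geometric means. Use percentage points for lasing activity.
- **Covariates.** Say that stone volume and number come from the pre-operative CT, since Section 5.1 does not list which measurements are taken. Do not carry over operative time from Section 9.3.2: it is measured after randomization and is itself one of the metrics.
- **Redundancy.** If the same stone volume is used in the metric and as the covariate, log fragmentation speed and log lasing time give the same arm effect with opposite sign. Count them as one result.
- **Zero lasing time.** Report the number per arm. Describe the lasing-based analyses as conditional on lasing, a group decided after randomization. Analyse operative time in all patients.
- **Biomarkers.** Reconcile Sections 7.2, 9.3.3 and 10.1.3 with the Synopsis, Section 1.3 and Section 3. Either remove the urine and biomarker text, or define the biomarkers, list them as an endpoint and schedule them.

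The cost is protocol and SAP wording, three degrees of freedom per model and a little more analysis work, using a CT that is already required. If urine is in fact collected, the schedule and consent text must be checked as well. The consent pages are not visible here.

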## **10 SUPPORTING DOCUMENTATION AND OPERATIONAL CONSIDERATIONS**

## 10.1 REGULATORY, ETHICAL, AND STUDY OVERSIGHT CONSIDERATIONS

## 10.1.1 INFORMED CONSENT PROCESS

The standard informed consent process for research outlined in SOP HRP-090 will be followed.

#### 10.1.1.1 CONSENT PROCEDURES AND DOCUMENTATION

Subjects will be recruited from [name] practice. Patients will be recruited during initial presentation to the office. Consent will be obtained at the initial office visit when decision to proceed to surgery has been made.

Potential subjects will be informed of the study at their preoperative visit (see above point) and may sign the consent at that time if they feel comfortable. If subjects require time for further contemplation, the consent may be signed on the day of surgery in the preoperative area (prior to administration of any anesthesia). This gives potential subjects at least 24 hours to consider the study and review the consent form.

Given the simplicity of the nature of subject involvement, we anticipate that no more than 5 minutes will generally be required to explain the consent form. However, longer and more extensive discussions will be available to those who request or require. All potential subjects will be verbally informed that their participation is completely optional and that their decision of whether or not to participate does not impact their care in any manner. Subjects will be asked to verbally repeat and summarize their involvement in the study. A copy of the consent form will be provided to the subject directly after signing the form.

# 10.1.2 CONFIDENTIALITY AND PRIVACY

The data will be housed in Mount Sinai's REDCap database. The data is anonymous, and no identifiers are collected. The data will be stored with protected passwords. The data will be reported to the sites in aggregate and anonymized. The publication will also not mention any center by name. The results in the publication will be in aggregate form and anonymous.

# 10.1.3 FUTURE USE OF STORED SPECIMENS AND DATA

The data will be deleted 6 years after publication, per regulations. Data will not be shared with any outside organizations. Urine specimens will be stored with identifiable information removed. After this removal, samples may be the information and/or samples may be used for future research studies or shared with other research teams for future research studies. Subjects will not be informed of the details of specific research that is done with the specimens.

# 10.1.3.1 DATA COLLECTION AND MANAGEMENT RESPONSIBILITIES

Data collection will be the responsibility of the research staff at the site under the supervision of the site investigator. The investigator will be responsible for ensuring the accuracy, completeness, legibility, and timeliness of the data reported.

Clinical data (including adverse events (AEs), concomitant medications, and expected adverse reactions data) and clinical laboratory data will be entered into REDCAP, a password protected, HIPPA compliant database.

The data safety will be monitored by the PI

# 10.1.3.2 STUDY RECORDS RETENTION

Study documents will be retained until at least 6 years have elapsed since the formal discontinuation of clinical development of the study intervention.

## 10.1.4 PROTOCOL DEVIATIONS

The study team will review protocol deviations on an ongoing basis and will implement corrective actions when the quantity or nature of deviations are deemed to be at a level of concern.

Protocol deviations will be sent to the reviewing Institutional Review Board (IRB) per their policies. The site investigator will be responsible for knowing and adhering to the reviewing IRB requirements.

#### 11 FUNDING

There is no funding for this study.

